8.1 Overall study structure

This is a multi-site phase II enrolment study. Centres participating in the study will include the four North West centres in the NWCOG, plus up to four others.

THE PRIMARY ENDPOINT is the histologically confirmed R0 resection rate.

THE SECONDARY ENDPOINTS are as follows:

- Radiotherapy compliance.
- Grade 3 or 4 toxicity.
- Pathological complete response
- Morbidity post operative and long term.
- Disease-free survival and local failure-free survival.

Patients will be assessed for eligibility prior to recruitment (see inclusion/exclusion criteria).

Treatment should be started as soon as possible after registration. The MRI scan that has been used for eligibility and disease evaluation needs to be within 35 days of registration. Patients should have an acceptable haematological and biochemical profile within 7 days of the first day of chemotherapy administration.

If blood tests and calculated GFR used to confirm eligibility are not within 7 days of treatment start, further testing will be required (see Section 9 for details). If the following were not included in routine investigations prior to registration, they too need to be obtained prior to the start of study treatment as part of the required baseline investigations: CEA, serum magnesium, clotting (see Section 9)

A calculated glomerular filtration rate (GFR) using the Cockroft Formula is acceptable but if this is less than 50 ml/min then a formal 24-hour urine collection or serum EDTA clearance should be carried out to determine GFR (see Appendix 4).

Before CRT begins, 2×10 ml blood samples will be collected from consenting patients. One sample will be used for testing for UGT1A1 polymorphisms and the other will be stored for future research studies (see Section 19). Patients will receive a six week (in total) course of treatment: week 1, cetuximab only; weeks 2 - 6 radiotherapy combined with cetuximab, irinotecan and capecitabine.

A defunctioning stoma will be fashioned for severe symptoms due to the primary tumour at the discretion of the treating team.

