A clinical evaluation will be carried out (doctor/nurse) at the commencement of cetuximab, every week during radiotherapy and for four weeks following completion of treatment to record blood count, biochemical profile, estimated GFR, and toxicity scores (using NCI CTC V.3.0). Serum magnesium is to be monitored weekly for 8 weeks post completion of cetuximab treatment. In patients on anticoagulants or those with an abnormal initial clotting profile, clotting profile is measured weekly during chemotherapy then weekly for four weeks post-termination (and longer if deemed clinically appropriate) if this is abnormal.

An MRI scan will be carried out at six weeks following radiotherapy completion then an attempt at surgery will take place eight weeks post radiotherapy completion.

Following surgery, adjuvant chemotherapy is given according to the discretion of the treating physician but recorded on the relevant CRF.

A sample of formalin-fixed paraffin-embedded tumour tissue removed during surgery will be sent to a central lab for analysis of KRAS mutation status. The tumour tissue will be stored and used in future research studies if the patient has consented to this. Otherwise, it will be returned to the site.

From the point of view of late toxicity, patients will be assessed at 6, 12, 24 and 36 months post completion of radiotherapy.

On confirmed tumour progression further formal follow-up within the trial ceases apart from ultimately recording date and cause of death. Further clinical management, including second-line chemotherapy is at the discretion of the treating physician. On study withdrawal for any reason then the CRF Off Study Form is completed, providing reason for treatment withdrawl and/or complete withdrawl. On patient death, CRF Death Form is (also) completed.

No other concomitant cytotoxic treatment or radiotherapy is permitted during the trial.

Specified dose limiting toxicities:

All toxicities below must adhere strictly to definitions specified in the National Cancer Institute Common Terminology Criteria for Adverse Events v3.0:

 Grade 3 diarrhoea that does not improve to grade 2 or less, within 24 hours on intensive anti-diarrhoeal therapy

- o Grade 4 diarrhoea
- Grade 3 or 4 fatigue
- Grade 3 or 4 neutropenia accompanied by fever (>38°C) or ≥grade 3 infection
- Grade 4 thrombocytopenia (platelet count < 25×10^{9} /L)
- o Grade 4 nausea/vomiting despite full antiemetic treatment

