Therefore local failure will be the time from randomisation to the first confirmation of local failure as defined above.

Local failure-free survival will be the time from randomisation to local failure or death whichever occurs first, survivors with no local recurrence being censored at the date last seen.

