10.1 Withdrawal from Trial Treatment

A patient may stop trial treatment for the following reasons:

- Progression whilst on therapy
- o Unacceptable toxicity
- o Intercurrent illness which prevents further treatment
- o Withdrawal of consent for treatment by patient
- Any alterations in the patient's condition which justifies the discontinuation of treatment in the investigator's opinion.

The reason should be recorded on the Treatment CRF and Withdrawal form.

The patient should however remain in the trial for the purposes of follow-up and data analysis, therefore, patients who withdraw from trial treatment for any reason other than disease progression and withdrawal of consent from trial including data collection, will continue to be followed-up for disease progression and late toxicity.

On confirmed tumour progression, further formal follow-up within the trial ceases apart from ultimately recording date and cause of death of death.

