to predict clinical benefit from cetuximab in locally advanced rectal cancer patients treated with neoadjuvant systemic chemotherapy followed by pre-operative chemoradiotherapy [1]. In particular, patient with *TP53* wild-type tumours had a significant survival benefit (in terms of both progression-free survival and overall survival) when cetuximab was added to standard therapy. Of note, this effect was independent of other variables including the tumour *RAS* status.

2. TP53 analysis

DNA will be extracted from sections which are representative of the tumour (i.e. contain more than 30-50% tumour cells if possible) according to standard laboratory procedures. The extracted DNA will be sent for mutational analysis to the Department of Molecular Diagnostics, Centre for Molecular Pathology, The Royal Marsden NHS Foundation Trust, [name].

The mutational status of *TP53* will be assessed by using a highly sensitive next generation sequencing (NGS) technique. This allows the simultaneous mutational analysis of four additional genes (including *KRAS*, *NRAS*, *BRAF* and *PI3KCA*) which are downstream of EGFR and could be potentially associated with the activity of cetuximab in this setting.

The mutational status of *TP53* and the above mentioned genes will be correlated with shortterm (tumour response to treatment and pathologic complete response rate) and long-term outcomes (local relapse-free survival, distant metastases-free survival, progression-free survival, overall survival) of the study population.

3. Rational for testing *FcyRlla-H131R* and *FcyRlla-V158F* single nucleotide polymorphisms in rectal cancer

Cetuximab may exert its antitumour activity by enhancing the mechanism of antibodydependent cellular cytotoxicity (ADCC). When the antigen-binding fragment (Fab) and the crystalline fragment (FC) of cetuximab engage the tumour cell antigen and a FC gamma receptor (FcγR) on an effector cell, respectively, immune cells (including monocytes, macrophages and activated natural killer (NK) cells) recognise and attack antibody-coated tumour cells. Single nucleotide polymorphisms in the coding regions of $Fc\gamma RIIA$ (C>T substitution at position 131 which changes the amino acid from histidine to arginine) and $Fc\gamma RIIIA$ (T>G substitution at position 158 which changes the amino acid from valine to phenylalanine) have been reported to modulate the anti-tumour activity of monoclonal antibodies.

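### Follow-up stops at any confirmed progression, so pelvic recurrences after a distant relapse go unrecorded although local failure and local failure-free survival still need them

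*Protocol*

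**What the plan says.** Section 8.1 names "Disease-free survival and local failure-free survival" as secondary endpoints and plans late-toxicity assessments at 6, 12, 24 and 36 months after radiotherapy. It then sets the stopping rule: "On confirmed tumour progression further formal follow-up within the trial ceases apart from ultimately recording date and cause of death".

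Section 10.1 has the same rule: "On confirmed tumour progression, further formal follow-up within the trial ceases apart from ultimately recording date and cause of death of death". Its preceding sentence keeps in follow-up only "patients who withdraw from trial treatment for any reason other than disease progression and withdrawal of consent from trial including data collection". The rule is therefore deliberate and not a slip in one place. Tumour progression is not defined or limited to the pelvis in either section.

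Section 9.2 defines the endpoint: "Local failure-free survival will be the time from randomisation to local failure or death whichever occurs first", with "survivors with no local recurrence being censored at the date last seen". It also defines a separate time to local failure, in which death is not an event. Local failure includes confirmed local recurrence found during follow-up. Distant metastasis is an event for disease-free survival only.

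All three definitions in 9.2 start at randomisation. Section 7 describes registration and allocation of a trial number, and section 8.1 describes a phase II enrolment study. No randomisation procedure exists.

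Appendix 4 plans to correlate tumour and germline markers with "long-term outcomes (local relapse-free survival, distant metastases-free survival, progression-free survival, overall survival", without defining these outcomes.

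**The concern.** The endpoint definition and the data-collection rule do not fit together. LFFS requires that a patient with metastases stays under observation for pelvic recurrence, and the stopping rule ends that observation. Take a patient with liver metastases at 12 months, pelvic recurrence at 18 months and death at 30 months. The correct LFFS time is 18 months and the recorded one is 30. In time to local failure, the same patient's event disappears.

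Distant-first failure is foreseen. Section 2.3 lists distant metastases among the important causes of failure, and 9.2 has a category for patients left unresected because of metastatic disease. Of the three ways in 9.2 to confirm a local recurrence, only the equivocal-imaging route requires that metastases be absent. Biopsy and unequivocal imaging remain open after a distant relapse, which is the period left unobserved.

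An analysis plan cannot recover events that were never collected. The same gap works in reverse for any outcome, such as distant metastases-free survival in Appendix 4, that needs distant status after a local failure.

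**Working it through.** **No figure to reproduce.** The protocol states no event rate or target for LFFS. Its sample-size calculation (section 13) concerns R0 resection and does not bear on this point.

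**What is recorded after a distant relapse**

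| Endpoint (9.2) | Distant relapse an event? | Later pelvic recurrence under 8.1 and 10.1 |
|---|---|---|
| Disease-free survival | Yes | Not needed; event already counted |
| Time to local failure | No | Lost |
| LFFS | No | Replaced by later death, or by censoring |

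**Inputs, all assumed:** 3-year local failure before relapse 10-15%; 3-year distant relapse 20-40%; local failure after distant relapse 2-30% per year; median survival after relapse 1-2 years; death without relapse at rate 0.01 per year; constant hazards; follow-up for vital status of 3 to 5 years.

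**Formulas.** Let a be the total hazard before any event, d the distant hazard, p the local hazard after relapse, m the death hazard after relapse, and b = p + m. With full recording,

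LFFS(3) = e^(-3a) + d[e^(-3a) - e^(-3b)]/(b - a).

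Under the stopping rule, with survivors censored when last known alive, b is replaced by m, because only death is seen after relapse.

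**Largest case** (local 10%, distant 40%, 30% per year after relapse, median survival 2 years):
- d = -ln(0.6)/3 = 0.1703; a = 0.0351 + 0.1703 + 0.01 = 0.2154; p = -ln(0.7) = 0.3567; m = ln(2)/2 = 0.3466; b = 0.7032.
- Full recording: 0.5240 + 0.1703 × (0.5240 - 0.1213)/0.4879 = 0.665.
- Protocol rule: 0.5240 + 0.1703 × (0.5240 - 0.3536)/0.1312 = 0.745.
- Error: about +8 points.

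**Smallest case** (local 10%, distant 20%, 2% per year after relapse, median survival 1 year):
- d = 0.0744; a = 0.1195; p = 0.0202; m = 0.6931; b = 0.7133.
- Full recording: 0.6987 + 0.0744 × (0.6987 - 0.1177)/0.5938 = 0.7715.
- Protocol rule: 0.6987 + 0.0744 × (0.6987 - 0.1250)/0.5736 = 0.7731.
- Error: about +0.2 points.

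**The other reading of the censoring date.** The date last seen could instead be the relapse visit. Deaths after relapse are then still counted while survivors leave the risk set at relapse, which pulls the estimate down and opposes the first effect. Kaplan-Meier estimates from simulation (at least 300,000 patients per scenario, same inputs) give about -2 to +5 points. The error is zero or negative at 2-5% local failure per year after relapse. It is about zero or upward at 10% and clearly upward at 20-30%. In the largest case above, the simulated values were 66.2% with full recording and 71.7% under this reading.

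**Local failures missed by 3 years.** With 10-30% local failure per year after relapse, the simulation gives about 1.6-12% of patients. For 80 patients this is 80 × 0.016 = 1.3 to 80 × 0.12 = 9.6.

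**The case against.** Deaths are still collected and death is an LFFS event, so in patients who die the event is delayed and not lost. This stands and bounds the error.

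A reader might infer that most of the local-control signal is hidden. For example, if 20-30% of 80 patients relapse distantly first and 20-40% of those later fail locally, 3.2 to 9.6 local failures are missed, which is 20-60% of an assumed 16. That describes missed local failures under assumed rates. It does not describe LFFS, whose error is the much smaller range above.

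A reader might also infer that LFFS is necessarily overstated. The text does not fix this: the direction depends on what the date last seen means and on how often pelvic recurrence follows relapse.

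Two of the three kinds of local failure in 9.2 arise at reassessment or laparotomy, largely before a post-operative relapse could stop follow-up. Only later recurrence is exposed.

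The biomarker analyses might seem biased upwards too. That does not follow: a shift in overall level distorts an association only if it differs by marker, and nothing in the protocol indicates this. The local relapse-free survival in Appendix 4 is also not shown to be the LFFS of 9.2.

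Finally, the decision on a phase III trial rests on R0 resection (section 13), and LFFS is a secondary endpoint. That limits the weight of the point, but it does not reconcile 8.1 and 10.1 with 9.2.

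**Conclusion.** The inconsistency is real and lies in the protocol's data-collection rule. Followed exactly, the protocol loses pelvic recurrences after distant relapse from time to local failure and misdates or censors them in LFFS. Under the assumed rates, the 3-year LFFS error is about +0.2 to +8 points with censoring at last known alive, and about -2 to +5 points with censoring at the relapse visit. These sizes rest wholly on assumptions, because the documents give no rates. Disease-free survival and R0 resection are untouched by the stopping rule.

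The randomisation wording in 9.2 is a genuine error for disease-free survival, local failure and LFFS. It is mainly one of wording: registration is the only entry event and treatment is to start as soon as possible afterwards, so the numerical effect should be small. It does not extend to the Appendix 4 outcomes, which have no stated time origin. The point merits correction as a matter for secondary endpoints.

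**What to change.** 1. In 8.1 and 10.1, after a distant progression keep recording the date and site of first local failure, and after a local failure the date and site of first distant failure. Take these from routine-care records on the existing follow-up CRF, to 36 months or death.
2. In 9.2, state that survivors are censored at the date their local status was last known. This alone is not enough: without item 1 that date is the relapse visit, and the -2 to +5 point range applies.
3. If local status after progression is not collected, report local failure as the cumulative incidence of first event, with distant progression and death as competing events. This answers a narrower question but uses only recorded data. The analysis plan, not shown here, may be the place for it.
4. In 9.2, replace 'randomisation' with 'registration' as time zero.

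Cost: protocol wording and a few CRF items, with no extra visits or scans. The downside is that local-failure dates after progression will depend on routine, unevenly timed imaging, since 9.1.5 requires only physical examination and late-toxicity assessment at follow-up visits.

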8.2 Treatment details

8.2.1 Treatment summary

Patients will be treated with pelvic radiotherapy to a planned volume at a dose of 45 Gy in 25 daily fractions of 1.8 Gy treating 5 days per week from Monday-Friday.

Concurrently they will receive oral capecitabine at 650 mg/m² bd 5 days per week from Monday-Friday on the days of radiotherapy only.

In addition, they will receive a loading dose of iv cetuximab at 400 mg/m² one week before the commencement of radiotherapy then at 250 mg/m² once per week during weeks 1, 2, 3, 4 and 5 radiotherapy i.e. six doses of cetuximab in total.

In addition they will receive iv irinotecan at 60 mg/m² once per week for four doses in total during weeks 1, 2, 3 and 4 of radiotherapy. Administration of irinotecan follows the administration of cetuximab.

Antiemesis: Prior to weekly treatments including iv irinotecan and cetuximab it is recommended that patients will receive premedication using a 5HT3 antagonist such as 8 mg iv ondansetron plus a steroid such as 8 mg iv dexamethasone (in addition they will receive an antihistamine such as 10 mg iv chlorpheniramine to reduce the likelihood of a cetuximab-related infusion reaction). Prior to treatment with iv cetuximab alone, it is recommended that patients receive an antihistamine plus steroid. Oral antiemetics following iv infusions including irinotecan might include dexamethasone for one or two days but otherwise antiemetics such as metaclopramide or domperidone are to be used as required according to standard local practice.

Patients may have a Hickman line or peripherally inserted central catheter (PICC) inserted at the physician's discretion if required to give adequate venous access for the administration of cetuximab and irinotecan. In these patients prophylactic warfarin should not be given because of the interaction between warfarin and capecitabine. Body surface area (BSA) will be calculated using actual body weight and no dose capping is carried out. No change in the dose calculation is carried out for obese patients.

No dose banding is carried out for irinotecan or cetuximab although it is for capecitabine (detailed in Section 8.2.2).

Instructions for storage use and handling of each drug should be according to each SmPC and hospital policies.

8.2.2 Capecitabine

Administration: Capecitabine is taken orally twice a day in equal doses for five days per week (Monday to Friday) throughout the 5 week course of radiotherapy. There is no capecitabine treatment on Saturday or Sunday. Patients will be asked to take the capecitabine approximately 12 hours apart as close to 8am-9am and 8pm-9pm each day within 30 minutes of the ingestion of food (ideally after breakfast and evening meal) with approximately 200 ml of water, with the first dose prior to radiotherapy on day 1. For patients who find swallowing capecitabine difficult it is possible to dissolve the tablets in lukewarm water. The capecitabine tablets should be placed in approximately 200 ml of lukewarm water. By stirring for about 15 minutes the tablets should dissolve. There is no stability data for any form of capecitabine suspension, so this should be done immediately prior to use and the solution swallowed immediately, rinsing to ensure that all the contents are ingested. As the solution will have a bitter taste it could be flavoured with a fruit juice or squash, but grapefruit juice should not be used. The solution may also be administered through a naso-gastric tube or other enteral feeding tube.

Capecitabine dose =	= 650 mg/m² bd	Number of tablets to be taken at each dose (morning and evening) Mon-Fri							
Surface area (m ²)	Twice daily dose (mg)	150 mg	500 mg						
< 1.46	900	6	-						
1.47-1.66	1000	-	2						
1.67-1.89	1150	1	2						
1.90-2.12	1300	2	2						
>2.13	1450	3	2						

Capecitabine dose calculation according to body surface area

Figure 12: Capecitabine dose banding at 650 mg/m²

Drug supply: Capecitabine will be available through routine medical supplies. Chemotherapy prescriptions should conform to local best practice including electronic prescribing systems where available. Capecitabine prescriptions to take home should include the exact number of tablets for that current cycle.

Capecitabine will require 'clinical trial' labelling by the site pharmacy in compliance with regulatory requirements, but no additional accountability records other than the pharmacy's standard tracking/dispensing log are required. Unused capecitabine should be disposed of as per hospital policy.

Capecitabine side effects: The side effect profile of capecitabine is similar to 5FU. The main toxicities are hand-foot syndrome, diarrhoea, nausea and stomatitis. Vomiting, fatigue, abdominal pain, dermatitis, fever, parasthesia, headache, dizziness, insomnia, anorexia and a drop in white blood cells are also experienced.

Occasionally, the following problems have been reported: taste disturbance, chest pain, angina pectoris, abnormal drowsiness or lethargy, weakness, dehydration and alopecia.

Capecitabine is contraindicated in patients with moderate or severe renal impairment. Antacids containing aluminium hydroxide may interfere with the absorption of capecitabine and so an alternative should be prescribed if possible.

Capecitabine precautions: Altered coagulation and/or bleeding have been reported in patients taking coumarin-derivative anticoagulants concomitantly with capecitabine. These events occurred within several days and up to several months after initiating capecitabine and also within one month of stopping capecitabine. Patients should be monitored regularly (twice weekly during CRT) for alterations in their coagulation parameters.

Phenytoin plasma concentrations have been shown to increase when used concomitantly with capecitabine. Again, patients should be regularly monitored for increase in phenytoin plasma concentrations and associated clinical symptoms.

Capecitabine should not be administered together with sorivudine [an antiviral] or its chemically related analogues such as brivudine. A chemically significant drug-drug interaction between sorivudine and 5FU, resulting from the inhibition of dihydropyrimidine dehydrogenase [DPD] by sorivudine has been described in literature. This interaction is potentially fatal as it leads to increased fluoropyrimidine toxicity.

It has been the experience of the Trial Management Group (TMG) in the NWCOG-2 trial that despite warnings of potential side effects, there sometimes remains in the patient's mind, the perception that because capecitabine is a tablet, it does not have the same potential to cause side effects as intravenous chemotherapy. It has to be emphasised to patients that oral chemotherapy has the same potential to cause side effects as intravenous chemotherapide to cause side effects as intravenous chemotherapy. It has to be emphasised to patients that oral chemotherapy has the same potential to cause side effects as intravenous chemotherapy and if rapidly worsening side effects are occurring, that they must stop the capecitabine tablets immediately and ring in to contact numbers for medical advice.

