5.1 Patient inclusion criteria

- Histologically confirmed rectal adenocarcinoma with lower (distal) limit ≤12 cm from the anal verge using rigid sigmoidoscopy
- Rectal Cancer staged with MRI as locally advanced:

Mesorectal fascia threatened (tumour ≤1mm from mesorectal fascia) Mesorectal fascia involved or breached

- Low tumours arising <5cm from the anal verge
- No evidence of metastatic disease
- No pre-existing condition which would deter radiotherapy, e.g. fistulas, severe ulcerative colitis (particularly patients currently taking sulphasalazine), Crohn's disease, prior adhesions
- Estimated GFR (using Cockroft-Gault formula) >50 ml/min. If this is less than 50ml/min a 24-hour urine collection for estimation of GFR is required or a serum EDTA clearance
- Absolute neutrophil count ≥ 1.5 x 10⁹/I. Platelets ≥ 100 x 10⁹/I, serum bilirubin <1.25 x upper limit of normal (ULN); serum transaminase(s) < 3 x ULN; serum ALP < 5 x ULN
- Fit to receive all study treatments
- Able to comply with oral medication
- WHO performance status 0 or 1
- Written informed consent

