8.4.9. Dose modification in the event of renal toxicity

Although neither cetuximab nor capecitabine is nephrotoxic, serum creatinine and calculated GFR should be monitored weekly during radiotherapy. If the calculated GFR deteriorates to 50 ml/min or below a formal measurement (24 hour urine or EDTA) is required. Dose reduce capecitabine as shown below. If GFR falls below 30 ml/min the patient should stop capecitabine.

Formal GFR	Radiotherapy	Capecitabine	Cetuximab	Irinotecan
> 50 ml	Continue	100%	100%	100%
30-50 ml	Continue	75%	100%	100%
< 30 ml	Continue	Do not give	100%	100%

Figure 8: Dose modification for renal toxicity

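### The capecitabine contraindication in Section 8.2.2 has no GFR values and does not clearly fit Figure 8, which gives 75% of the dose at a formal GFR of 30-50 ml/min

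*Protocol*

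**What the plan says.** Three places in the protocol bear on capecitabine and renal function.

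- **Section 8.2.2, under side effects:** "Capecitabine is contraindicated in patients with moderate or severe renal impairment". No GFR value is attached to either grade, and the sentence is not limited to starting treatment.
- **Section 8.4.9 and Figure 8:** GFR is calculated weekly during radiotherapy, and "If the calculated GFR deteriorates to 50 ml/min or below a formal measurement (24 hour urine or EDTA) is required". The text continues: "Dose reduce capecitabine as shown below. If GFR falls below 30 ml/min the patient should stop capecitabine". The columns of Figure 8 are radiotherapy, capecitabine, cetuximab and irinotecan, in that order. The middle row reads "30-50 ml Continue 75% 100% 100" and the lowest row "< 30 ml Continue Do not give 100% 100". Above 50 ml, all drugs stay at 100%.
- **Section 5.1 (eligibility):** the estimated GFR by the Cockcroft-Gault formula must exceed 50 ml/min. Then: "If this is less than 50ml/min a 24-hour urine collection for estimation of GFR is required or a serum EDTA clearance". The value that the formal measurement must reach is not restated, either there or in Sections 8.1 and 9.1.1, which repeat the instruction to measure.

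**The concern.** Section 8.2.2 bars capecitabine in two grades of renal impairment. Figure 8 withholds it in one GFR band only, and the band above it receives the drug at a reduced dose. If that middle band includes what Section 8.2.2 means by moderate impairment, the protocol gives opposite instructions for the same patient.

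Two things are at stake. The first is safety. Section 8.2.2 lists diarrhoea among the main toxicities of capecitabine, and Section 13 names it as the most common serious toxicity of irinotecan-containing chemoradiation regimens. The second is consistency across the six to eight centres foreseen in Section 3.1. Section 16.1 asks sites to report every protocol deviation, and Section 14.2 looks for dose modifications that were not observed. Neither can be judged evenly while two sections can be read to require different doses.

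**Working it through.** The protocol states no figure to reproduce, so the check is a side-by-side comparison by GFR band.

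| Formal GFR (Figure 8) | Capecitabine under Section 8.4.9 / Figure 8 | Capecitabine under Section 8.2.2 |
|---|---|---|
| above 50 ml | 100% | not barred, unless this band includes moderate impairment |
| 30-50 ml | 75% | barred for any part of the band that is moderate or worse; otherwise not barred |
| below 30 ml | do not give | barred, if this band is moderate or severe |

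**Step 1. When do the two sections agree?** Only if moderate and severe impairment both lie wholly below 30 ml/min. The whole 30-50 band must then be milder than moderate.

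**Step 2. Does the protocol say that?** No. Figure 8 does not use the words mild, moderate or severe, and no section ties them to a GFR value. What the protocol does show is that it treats the 30-50 band as impaired enough to need a formal measurement and a dose cut of 100% − 75% = 25%. In a table with a full-dose band, a reduced-dose band and a no-drug band, it is natural to read the middle band as the middle grade. That is an inference, and it is the assumption on which the conflict rests.

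**Step 3. What is the difference under that assumption?** The planned dose is 650 mg/m² twice daily. Figure 8 gives 0.75 × 650 = 487.5 mg/m² twice daily, before dose banding. Section 8.2.2 gives none. The gap is 75% of the planned dose for as long as the patient stays in the band.

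**Step 4. Can a patient reach this band?** Yes. Weekly calculated GFR, with a formal measurement at 50 ml/min or below, is a defined route into it during treatment. How many patients would take that route cannot be worked out from the protocol.

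**The case against.** Three arguments can be made on the other side.

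**The grades are undefined, so no contradiction is proved.** This stands in part. A reader might infer that the table itself settles the matter and that moderate must mean 30-50 ml/min. The protocol does not support that. Calling 30-50 mild and everything below 30 moderate or severe would be consistent with both sections, because two grades that share one instruction do not need two rows. The conflict is therefore conditional. The missing definition is still a defect: a contraindication without GFR values cannot be applied uniformly.

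**The sections do different jobs.** Section 8.2.2 can be read as a general bar on treating patients who already have renal impairment, and Section 8.4.9 as the specific rule when function falls during treatment. A site managing a falling GFR would turn to 8.4.9, where text and table agree. The reading is plausible, but Section 8.2.2 does not make the distinction. The protocol can make such a link when it wants to: Section 8.2.4 ties irinotecan to the eligibility limits for hepatobiliary function during treatment. No similar wording connects 8.2.2 to 8.4.9.

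**Section 5.1 already keeps such patients out.** This largely stands. A reader might infer that, because no minimum is given for the measured value, the trial admits patients with a measured GFR below 50. The ordinary reading is that the threshold of more than 50 ml/min carries over to the formal measurement, which would otherwise have no purpose at entry. What remains is a small drafting gap and not a second conflict.

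**Conclusion.** The concern holds as a conditional inconsistency. Section 8.2.2 bars capecitabine in moderate or severe renal impairment without giving values or saying when the bar applies. Section 8.4.9 and Figure 8 give the drug at 75% for a formal GFR of 30-50 ml/min and stop it only below 30. On the assumption that some part of the 30-50 band is moderate, the two cannot both be followed, and a patient there could receive either 0% or 75% of the planned dose. Without that assumption, the relation between the two sections is still unclear to a site.

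If the entry threshold carries over to the measured value, only patients who deteriorate during treatment are affected. Their number is unknown. The sample size and the primary analysis of R0 resection are not affected.

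A reader might also infer that Section 8.2.2 is the correct rule and that Figure 8 should be changed to match it, or the reverse. The protocol gives no basis for either choice, and none is made here.

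**What to change.** Reconcile Section 8.2.2 with Section 8.4.9 and Figure 8 so that all of them give one instruction for any GFR:

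- express the contraindication in Section 8.2.2 in GFR values;
- say whether it applies at entry, on treatment or both;
- check that the text and Figure 8 in Section 8.4.9 are consistent with the result, whichever rule the sponsor adopts.

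As a minor clarification, state in Section 5.1 the threshold against which the formally measured GFR is tested.

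The clinical rule itself is for the sponsor to decide. The cost is protocol wording only, with no change to the design, the sample size or the analysis.
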